**LIST OF ABBREVIATIONS AND RELEVANT DEFINITIONS**

ABR	General Assessment and Registration form (ABR form), the application form that is required for submission to the accredited Ethics Committee; in Dutch: Algemeen Beoordelings- en Registratieformulier (ABR-formulier)
AE	Adverse Event
AR	Adverse Reaction
CA	Competent Authority
CCMO	Central Committee on Research Involving Human Subjects; in Dutch: Centrale Commissie Mensgebonden Onderzoek
CV	Curriculum Vitae
DSMB	Data Safety Monitoring Board
EU	European Union
EudraCT	European drug regulatory affairs Clinical Trials
GCP	Good Clinical Practice
GDPR	General Data Protection Regulation; in Dutch: Algemene Verordening Gegevensbescherming (AVG)
IB	Investigator's Brochure
IC	Informed Consent
IMP	Investigational Medicinal Product
IMPD	Investigational Medicinal Product Dossier
METC	Medical research ethics committee (MREC); in Dutch: medisch-ethische toetsingscommissie (METC)
(S)AE	(Serious) Adverse Event
SPC	Summary of Product Characteristics; in Dutch: officiële productinformatie IB1-tekst
Sponsor	The sponsor is the party that commissions the organisation or performance of the research, for example a pharmaceutical company, academic hospital, scientific organisation or investigator. A party that provides funding for a study but does not commission it is not regarded as the sponsor but referred to as a subsidising party.
ADE	Adverse Device Event
UAVG	Dutch Act on Implementation of the General Data Protection Regulation; in Dutch: Uitvoeringswet AVG
WMO	Medical Research Involving Human Subjects Act; in Dutch: Wet Medisch-wetenschappelijk Onderzoek met Mensen

## SUMMARY

**Rationale:** Current manual diuresis monitoring is labour intensive, to optimally monitor hospitalised patients with a urine catheter. The automated FlowSure monitor aims to automate diuresis monitoring and data processing to the electronic medical record.

**Objective:** The primary endpoint is the *accuracy* of urine production monitoring using the automated FlowSure monitoring compared to the standard manual method of monitoring.

**Study design:** Part A is single arm intervention study in which patients will receive *both* the manual monitors and automated FlowSure monitor (both devices will be used in conjunction).

Part B is a two-arm randomized non-blinded intervention study in which patients will be monitored with *either* the manual monitoring or automated FlowSure monitor.

**Study population:** Patients admitted to the hospital who ~~-~~ for medical reasons unrelated to the study have a urine catheter inserted.

**Intervention (if applicable):** in part A patient will undergo double urine monitoring as they receive both the manual urine monitor and automated FlowSure monitor.

In part B patients will be randomized to monitoring with the manual monitor or to automated monitoring with the automated FlowSure monitor.

**Main study parameters/endpoints:** The primary outcome event in Part A will be the *accuracy* of urine measurement over two set time intervals (a nursing shift of 8 hours and a full 24-hour period) using manual monitoring and automated monitoring.

The measurements of both the manual and the automated urinemonitor will compared against the golden standard: the total urine production measured in a measuring cup by draining the collection bag.

The primary outcome in part B of the study will accuracy of measurement over a set time interval (a nursing shift of 8 hours and a full 24-hour period) using manual monitoring *and* automated monitoring. Therefore, the completeness of the hourly diuresis registration will be compared between the manual and automated measurement groups.

**Nature and extent of the burden and risks associated with participation, benefit, and group relatedness:** There is no direct benefit for patients participating in the study. The societal/research benefit of the study lies in the potentially improved diuresis monitoring and registration in the medical record of the patient which will improve the quality, (costs) effectiveness and accuracy of patient monitoring and therefore patient safety.

**Risks:** The foreseeable added risks associated with the use of FlowSure in Part A are negligible as using the automated monitor will be additive to the manual measurements.

In part B the patient will be monitored with either a manual monitor or the automated FlowSure monitor. If either monitor fails, the hourly urine production can be estimated by dividing the total urine collection since monitoring started by the hours that have passed since insertion of the urine catheter.

Risk-benefit analysis: Since the expected clinical-scientific benefit of this study is estimated as large and the clinical investigation is, in the opinion of the investigators, proportional to the added risk associated with the use of the medical device, which is estimated as low, the overall risk-benefit profile of the study is favourable.

## 1. INTRODUCTION AND RATIONALE

Diuresis, the amount of hourly produced urine, is a vital parameter that is routinely measured in patients hospitalized patients. Up to half of the millions of patients hospitalized each year in nursing wards and all intensive care unit patients and those undergoing surgery have an indwelling urine catheter inserted into the bladder in order to continuously measure urine production. A reduced diuresis of for example less than 30 millilitres per hour is the first sign of hemodynamic and clinical instability of the patient that can be the result of a (occult) bleeding, infection, or heart failure.

The first response of the body to mitigate hemodynamic instability is to retain fluid by decreasing diuresis. The traditional monitors are insufficient as reading and registering diuresis manually every hour for every patient is burdensome for nurses and often deprioritized due to time constraints. Unlike most other vital parameters, diuresis cannot simply be measured instantly like heart rate or blood pressure but requires monitoring over time which complicates registration. Hourly diuresis registration often is incomplete as nurses are unable to register at set times: a nurse assisting one patient cannot register urine production at the same time of the other patients under his or her watch.

As a result, information about the vital parameter diuresis is often not available when the clinical situation of the patient deteriorates and therefore compromising the patient safety. With accurate and complete information regarding changes in diuresis that prompt automated alerts, a clinical deterioration of the patient's condition will be detected earlier and intervened upon sooner, without an extra burden/time costing intervention of the nurse.

The automated FlowSure monitor is a digital hanging scale that continuously weighs urine production over time, as urine flows through the urine catheter into the catheter bag underneath the patient's bed. FlowSure visualizes the most recent hourly urine production on the screen of the medical device and transmits the generated data to the patient's electronic medical record.

Since the specific weight of urine is equal to water and thus one gram is equal to one millilitre, the increase in weight of the urine bag over time is a surrogate for urine production.

## FlowSure

The FlowSure does not come into contact with the patient or the patient's urine(bag), nor in contact with the nurses' hands for detection or view of the volume.

The urine flows from the bladder through the catheter into the catheter bag under the patient's bed, while the catheter bag is attached to the FlowSure.

Instead of attaching the urine bag to the bed, the urine bag is attached to the FlowSure so that the weight can be continuously measured and recorded.

Since FlowSure does not come into contact with the patient or the urine, it is *reusable* after surface disinfection of the medical device. The reusability will make the FlowSure cost effective to operate.

The FlowSure aims to achieve two goals:

1. Improving patient safety by providing complete registration of urine production with automated alerts
2. Reducing the workload for nurses by automating and directly registering urine production in the electronic medical record.

Figure 1: the traditional manual urine monitor.

[figure not shown]

Figure 2: computer aided design of the intended demonstrator second generation FlowSure prototype

### Preclinical research

The FlowSure team has conducted a non-human study at the cardiology department of the Amsterdam UMC. In the study we have demonstrated the functionality and accuracy of the device in a mock set-up. In the set-up a Braun infusion pump was used to simulate a patient with diuresis and the investigational FlowSure device was tested for operability, accuracy, and safety. The results demonstrated that the measurement with FlowSure is more accurate than the Braun infusion pumps that are currently in use in our hospital. The infusion pump was set at a fixed rate of 50 millilitres per hour. The golden standard was the manual measurement with a measuring cup. The accuracy of the FlowSure was within 1% margin from the golden standard, whereas the margin for the infusion pump is up to 10%.

## 2. OBJECTIVES

The objective of the study is in part A of the study protocol to demonstrate that in clinical care the investigational FlowSure device is able to monitor urine production accurately and safely. The aim in part B of the study is to demonstrate that the use of the investigational FlowSure device will result in more complete and (cost effective) urine production registration.

### 3. STUDY DESIGN

The study will consist of two parts. Part A is single arm intervention study in which patients will receive both the manual monitors and automated FlowSure monitor (both devices will be used in conjunction). Part B is a two-arm randomized non-blinded intervention study in which patients will be monitored with either the manual monitoring or automated FlowSure monitoring.

In both part A and part B the study will last for duration that the patient has a urine catheter inserted with a maximum of 24 hours. The setting of the study will be hospitalized patients who - for medical reasons unrelated to the study - have a urine catheter inserted.

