##### Inclusion criteria

In order to be eligible to participate in this study, a subject must meet all of the following criteria:

- 18 years and older
- Currently hospitalized
- Medical reasons unrelated to the study have a urine catheter inserted
- No specific urology problems
- Will and able to provide informed consent

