### 7.1 Study parameters/endpoints

#### 7.1.1 Main study parameter/endpoint

The primary outcome event in Part A will be the accuracy of urine measurement over two set time intervals (a nursing shift of 8 hours and a full 24-hours period) using manual monitoring and automated monitoring. The golden standard is the total urine production measured in a measuring cup by draining the collection bag in comparison with the new FlowSure device. The primary outcome in part B of the study will be the completeness of the hourly diuresis registration will be compared between the manual and automated measurement groups.

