### 7.4 Replacement of individual subjects

Subject who withdraws consent, will be replaced until the sample size of the study has been reached without changing the randomization parameters, there will be no reuse of previous allocations. In addition, participants may also be replaced in cases where the primary endpoint cannot be evaluated due to demonstrable deviations from study procedures. Such cases include, but are not limited to:

- Disposing of the reference standard prematurely without the presence of a study investigator
- Demonstrably incorrect handling or operation of the investigational device.

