### 9.2 Primary study parameter(s)

The primary outcome parameter of this study is the completeness of hourly urine production registration. It refers to the extent to which the two devices, the manual urine monitor and the FlowSure device, accurately capture and record hourly urine production data over a 24-hour period.

Completeness of hourly urine production registration represents the proportion or percentage of the total hourly measurements that are successfully recorded by each device.

For example, if a patient's urine output is measured every hour for 24 hours, the completeness rate indicates how many of these hourly measurements are successfully captured by the device.

In this study, the primary objective is to compare the completeness of hourly urine production registration between the manual urine monitor and the FlowSure device as registered in the electronic health record. The manual urine monitor has an assumed completeness rate of approximately 50% of hourly registrations, while Device B (FlowSure) is expected to have a higher completeness rate of over 90%.

By assessing the primary outcome parameter, the study aims to determine whether the FlowSure device significantly improves the completeness of hourly urine production registration, as compared to the manual urine monitor. The primary outcome will provide crucial insights into the devices' ability to accurately capture and register hourly urine production data, which is vital for monitoring and managing various clinical conditions.

The completeness of hourly urine production registration serves as a key indicator of the devices' reliability, usability, and potential clinical utility and safety. The primary outcome parameter will be analysed statistically, as described earlier, to assess the significance of the observed difference in completeness rates between the two devices.

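### A full 24-hour value is a Part A primary outcome, yet participation stops at catheter removal, no criterion asks for 24 hours of expected catheter time, and early removals are not replaced; Part B leaves its denominator open for the same patients

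*Combined protocol and SAP*

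**What the plan says.** Section 3 sets the length of participation for both parts: "the study will last for duration that the patient has a urine catheter inserted with a maximum of 24 hours".

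Section 7.1.1, in line with the Summary, asks in Part A for accuracy over two intervals: "a nursing shift of 8 hours and a full 24-hours period". The reference is the drained collection bag, measured in a cup.

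For Part B, section 9.2 describes completeness as the extent to which the devices "accurately capture and record hourly urine production data over a 24-hour period". It then defines it as "the proportion or percentage of the total hourly measurements that are successfully recorded by each device", with an illustration: "if a patient's urine output is measured every hour for 24 hours, the completeness rate indicates how many of these hourly measurements are successfully captured".

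On catheter time, the inclusion criteria ask only this: "Medical reasons unrelated to the study have a urine catheter inserted". The exclusion criteria in 4.2 rule out patients without a catheter but say nothing about a removal that is already planned.

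On replacement, section 7.4 says: "Subject who withdraws consent, will be replaced until the sample size of the study has been reached". It adds patients whose primary endpoint cannot be evaluated because of demonstrable departures from study procedures. Section 7.3 lets data collected before withdrawal be used. Sections 4.3, 9.1 and 9.2 contain no allowance or rule for patients observed for less than 24 hours.

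**The concern.** The cap on observation and the length of the outcome window are the same number, so any removal before the cap leaves the window unfilled. A patient enrolled a few hours before removal is eligible, follows the protocol fully, and still cannot supply the Part A 24-hour comparison.

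In Part A this leaves one of the two primary intervals with an unknown and smaller number of patients than the 25 planned. Those who contribute are the ones whose clinical course kept the catheter in. Part A also governs entry to Part B: item e of the structured risk analysis requires FlowSure to be within 15% of manual monitoring, without saying over which interval or in how many patients.

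In Part B the same patients have a shorter record, and the plan does not say how to score it. The trial is not blinded, so a denominator left open could be chosen after the data are known.

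**Working it through.** **1. Does the text admit patients who cannot give the outcome?**
- Section 3: participation ends at removal, and at 24 hours at the latest.
- Section 7.1.1: a full 24-hour value is needed in Part A.
- Inclusion and exclusion criteria: a catheter is in place now; no expected duration.
- Section 7.4: replacement for withdrawn consent or for a procedural deviation. Its list of cases is open-ended, but only as examples of deviations. Ending at removal is what section 3 prescribes, so it is neither ground.

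Such patients are therefore eligible, lack the 24-hour value and are not replaced. Removal between 8 and 24 hours costs the 24-hour value only. Removal before 8 hours costs both.

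**2. Size in Part A.** Input: 25 patients (4.3). The share f removed before 24 hours is not in the documents; 10-40% is assumed.

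Expected 24-hour values = 25 × (1 − f). Interval width relative to the plan = √(25/n), for equal spread.

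| f | 24-hour values | relative width |
|---|---|---|
| 10% | 22.5 | √(25/22.5) = 1.05 |
| 20% | 20 | √(25/20) = 1.12 |
| 30% | 17.5 | √(25/17.5) = 1.20 |
| 40% | 15 | √(25/15) = 1.29 |

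**3. Size in Part B under the two readings.** Inputs: 50% manual and 90% FlowSure (4.3, 9.2). Assume a share f is removed at hour t, equally in both arms.

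*Fixed denominator of 24:* each rate is multiplied by m = (1 − f) + f × t/24.

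| f, t | m | FlowSure vs manual | difference |
|---|---|---|---|
| 20%, 12 h | 0.80 + 0.10 = 0.90 | 81% vs 45% | 36 points |
| 40%, 12 h | 0.60 + 0.20 = 0.80 | 72% vs 40% | 32 points |
| 20%, 8 h | 0.80 + 0.067 = 0.867 | 78% vs 43.3% | 34.7 points |
| 40%, 8 h | 0.60 + 0.133 = 0.733 | 66% vs 36.7% | 29.3 points |

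For one FlowSure patient with every hour recorded until removal at 12 hours, the score is 12/24 = 50%, which is the rate assumed for manual monitoring.

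*Monitored hours as denominator:* the expected rates stay at 90% and 50% in every row, and that patient scores 12/12 = 100%.

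**4. Effect on Part B power, fixed 24 only.** The plan's figure of about 99% comes from its stated standard error: 0.40/0.0948 = 4.22 and Φ(4.22 − 1.96) = 0.988. With the pooled proportion 0.70 and 25 per arm, the standard error is √(0.70 × 0.30 × 2/25) = 0.130, and the usual two-proportion power is 0.895. That discrepancy is a separate matter; 0.895 is only the starting value here. On that framing, which treats each patient as one yes/no result, power falls to 0.77 (20% at 12 h) or 0.63 (40% at 12 h).

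Section 9.2 defines a proportion per patient, however. Simulating per-patient proportions, with a Welch t-test and an assumed within-patient correlation of 0.05-0.6, gives about 95% to over 99% (20% at 12 h), about 91% to over 99% (40% at 12 h) and about 81% to 97% (40% at 8 h). All stay above the 80% target in 4.3.

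**The case against.** **Part B reads naturally without the problem.** The operative definition in 9.2 is a share of the total hourly measurements, and 24 slots appear only in a conditional example. Section 3 ends the study at removal, after which no measurement is due. This stands. A reader might infer that the plan as written counts hours after removal as missed. The documents do not say so, and monitored hours is at least as natural a reading. What remains is that the reference to a 24-hour period leaves the other reading available.

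**Part B would survive even a fixed 24.** Equal early removal leaves the ratio unchanged (81/45 = 90/50 = 1.8) and shrinks the difference, which is conservative. A reader might infer from 0.77 or 0.63 that Part B is underpowered. Those values rest on a yes/no outcome that 9.2 does not define and on an assumed removal rate, so the documents do not support that inference.

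**Part A loses precision, and bias is not shown.** Accuracy is judged within each patient against the cup, and nothing in the documents suggests that a hanging scale errs differently in patients who recover sooner. A reader might infer a biased 24-hour result; no mechanism for it is given. Part A also has no power target to miss, because 25 is a judgement. All this stands, but a primary value that is missing without any rule is still a gap. Section 7.3 does not close it: it concerns withdrawn subjects and does not say how a 10-hour record is compared.

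**An eligibility line is itself selection.** True, and it narrows the population. But it acts before enrolment and, in Part B, before allocation, so it does not bias the comparison between arms.

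**Conclusion.** The concern holds for Part A. Following the protocol as written enrols patients who cannot supply one of its two primary values, and does not replace them. With an assumed early-removal rate of 10-40%, about 15-22 of 25 patients give a 24-hour value, and intervals are about 5-29% wider if the spread is unchanged. Removals before 8 hours reduce the 8-hour result as well. The harm is mainly precision, and its true size cannot be fixed because no removal rate is given.

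For Part B the finding is limited to a denominator that is not stated. The dilution from 40 to 36 points (20% removed at 12 hours) applies only if the denominator is a fixed 24, and it disappears if monitored hours are used.

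The plan should be changed because a primary outcome is exposed and the repair is cheap.

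**What to change.** 1. **Eligibility.** Add an inclusion criterion: *catheter expected to remain in place for at least 24 hours after the start of monitoring*.
2. **Part A (7.1.1 and 7.2).** Expectation is no guarantee, so add: if the catheter is removed early, take the cup reading at removal and compare both monitors with it over the elapsed time. Report how many patients contribute to the 8-hour, 24-hour and elapsed-time comparisons.
3. **Part B (9.2).** State that completeness is the number of hours recorded divided by the number of hours with the catheter in place and monitoring running, up to 24.

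The cost is one eligibility line, one measurement rule and one denominator sentence. Recruitment may be slightly slower, and the results would apply to patients expected to stay catheterised for 24 hours. None of this changes when a catheter is removed, which remains a clinical decision.

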### 4. STUDY POPULATION

#### 4.1 Population (base)

Patient will be drawn from our hospital wards including but not limited to the general cardiology ward, cardiac care unit (CCU).

##### Inclusion criteria

In order to be eligible to participate in this study, a subject must meet all of the following criteria:

- 18 years and older
- Currently hospitalized
- Medical reasons unrelated to the study have a urine catheter inserted
- No specific urology problems
- Will and able to provide informed consent

#### 4.2 Exclusion criteria

A potential subject who meets any of the following criteria will be excluded from participation in this study:

- Do not have a urine catheter inserted
- Are known to have chronically no diuresis (e.g., patients on dialysis) or other urology problems.
- A diuresis of <30ml per hour.

### 4.3 Sample size calculation

Part A will consist of 25 patients. Since this is the first-in-human study, to establish safety, and initial efficacy the investigators believe that this number will provide us meaningful information to collect scientific data for further development.

Part B will consist of 25 patients monitored with a manual monitor and 25 patients monitored with the FlowSure. The completeness of hourly urine production registration between the manual urine monitor and the FlowSure was compared using a two-group comparison of proportions. The study enrolled a total of 50 patients, with 25 patients using the manual urine monitor and 25 patients using the FlowSure. The completeness rate for the manual urine monitor was approximately 50% ( $P_1 = 0.50$ ), while the FlowSure data collection demonstrated a higher completeness rate of >90% ( $P_2 = 0.90$ ).

To assess the statistical significance of the difference in completeness rates, a significance level (alpha) of 0.05 was employed. The power (1 - beta) was set at 0.8. The pooled proportion (P) was calculated to be 0.70, and the standard error (SE) was estimated as 0.0948. Using a z-score of 1.96 for the selected alpha level, the difference in completeness rates was determined to be 0.40.

The effect size (ES), calculated by dividing the difference in completeness rates by the standard error, was found to be 4.216. Consequently, the study had a power of approximately 99% to detect the assumed difference in completeness rates between the manual urine monitor and the FlowSure monitoring device.

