### **6.2 Summary of findings from clinical studies**

This will be the first in human study to use the automated urine monitor FlowSure. Therefore, there is no previous experience to draw from, than a comparison with the manual method.

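### The standard error of 0.0948 and the 99% power for Part B do not follow from 25 versus 25 patients at 50% versus 90%; the named tests give about 83% to 91%

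*Combined protocol and SAP*

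**What the plan says.** Section 4.3 (Sample size calculation) sets the size of Part B: "Part B will consist of 25 patients monitored with a manual monitor and 25 patients monitored with the FlowSure". The planning rates are given as results: "The completeness rate for the manual urine monitor was approximately 50" per cent, and "while the FlowSure data collection demonstrated a higher completeness rate of >90" per cent, entered in the calculation as P1 = 0.50 and P2 = 0.90. The error rates are "a significance level (alpha) of 0.05 was employed", with z = 1.96 (hence two-sided), and "The power (1 - beta) was set at 0.8".

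The calculation then states: "The pooled proportion (P) was calculated to be 0.70, and the standard error (SE) was estimated as 0.0948". The difference of 0.40 divided by this standard error is reported as 4.216, and the section ends: "Consequently, the study had a power of approximately 99% to detect the assumed difference in completeness rates".

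Section 9.1 names the chi-square test or Fisher's exact test for the comparison, without choosing between them and without mentioning a continuity correction. Section 9.2 describes the 50% as assumed and the 90% as expected. Section 6.2 says of the device that "there is no previous experience to draw from" other than comparison with the manual method.

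**The concern.** All the inputs are printed, so the standard error can be recomputed, and 0.0948 is too small for 25 patients per arm. The ratio and the power are both built on it. This is the only quantitative justification for the size of Part B, and it concerns that part's primary outcome.

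At stake is how the trial's sensitivity is understood. The ethics committee and later readers are told that a true 40-point difference would be missed about once in a hundred trials. If the real figure is nearer one in six to one in eleven, a non-significant result carries much less weight against such a difference than the protocol implies.

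A smaller, related matter is wording. Section 4.3 reports enrolment and completeness rates in the past tense, as if observed, in a study it also calls first-in-human. A reader could take planning assumptions for data.

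**Working it through.** **Inputs** (Section 4.3 unless noted): n = 25 per arm; P1 = 0.50; P2 = 0.90; difference 0.40; pooled P = (0.50 + 0.90)/2 = 0.70; two-sided alpha 0.05, z = 1.96; tests from Section 9.1. Each patient counts as one binary outcome, as in the protocol's calculation.

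**1. The plan's own chain**
- 0.0948 is √0.009 = 0.09487, cut to four decimals. 0.40 / 0.09487 = 4.216, as stated.
- Power = Φ(4.216 − 1.96) = Φ(2.256) = 98.8%, the stated 99%.

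Everything after the standard error is therefore consistent. The standard error is the faulty step.

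**2. The standard error at 25 per arm**
- Pooled: √(0.70 × 0.30 × (1/25 + 1/25)) = √0.0168 = 0.1296
- Unpooled: √((0.50 × 0.50 + 0.90 × 0.10)/25) = √0.0136 = 0.1166
- One-arm form, in case that was used: √(0.21/25) = 0.0917

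None gives 0.0948. Solving for the sample size that would:
- Pooled: n = 0.42 / 0.0948² = 46.7, about 47 per arm
- Unpooled: n = 0.34 / 0.0948² = 37.8, about 38 per arm

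**3. The corrected ratio**
- 0.40 / 0.1296 = 3.09 (pooled); 0.40 / 0.1166 = 3.43 (unpooled)

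**4. Power at 25 per arm, two-sided 0.05**

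The usual normal approximation uses the pooled standard error under the null and the unpooled one under the alternative: Φ((0.40 − 1.96 × 0.1296)/0.1166) = Φ(1.25) = 89.5%.

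Exact power sums the probabilities of all 26 × 26 possible tables in which the test gives p ≤ 0.05.

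| Method | Power | Chance of missing the difference |
|---|---|---|
| Fisher's exact test, exact | 83.3% | 16.7% |
| Chi-square with continuity correction, exact | 83.0% | 17.0% |
| Chi-square without correction, exact | 91.1% | 8.9% |
| Normal approximation, pooled and unpooled | 89.5% | 10.5% |
| Normal approximation, pooled only | 87.0% | 13.0% |
| Normal approximation, unpooled only | 92.9% | 7.1% |
| Arcsine approximation | 90.6% | 9.4% |
| Normal approximation, continuity-corrected | 81.8% | 18.2% |

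One-sided versions of the normal approximations give 92.5% to 96.3%. No variant comes within 2 points of 99%.

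**5. Sample size for given power**
- 80%: 20 per arm by normal approximation, 25 with continuity correction. The protocol's target is met.
- 99%: 44 per arm by normal approximation; 47 per arm for exact Fisher power.

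**The case against.** The best counter-argument concerns the endpoint. Section 9.2 defines completeness as a proportion of hourly measurements, and no section sets a cut-off that would make a patient complete or incomplete. For a score between 0 and 1 with mean p, the yes/no case has the largest possible variance, p(1 − p). A comparison of mean per-patient completeness could therefore be more precise than the figures above. As an illustration, assume 24 readings per patient and the same within-patient correlation ρ in both arms. The unpooled variance is then multiplied by (1 + 23ρ)/24. At ρ = 0.5 the standard error is 0.084 and power by normal approximation is 99.7%; at ρ = 0.7 they are 0.098 and 98.2%. This stands as a limit on the conclusion: the 9% to 17% belongs to the binary calculation that the protocol presents. It does not rescue the 0.0948, because the protocol gives no correlation or between-patient standard deviation, and Section 9.1 names tests of proportions, not of means.

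The text also says more than 90%, so 0.90 could be a floor. But the calculation sets P2 = 0.90, and the pooled 0.70 confirms it. At an assumed 0.95, power would be 95.2% (Fisher) or 98.1% (uncorrected chi-square), still short of 99%.

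Two smaller points are fair. A target of 80% does not contradict a higher achieved power; the text merely fails to say which figure is which. The past-tense wording is a drafting fault, softened by Section 9.2 and by Section 4.3's own closing reference to an assumed difference. The statement in Section 6.2 concerns the new device, not the 50% for manual monitoring.

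**Conclusion.** The stated standard error, ratio and power are wrong as written. For 25 versus 25 patients at 50% versus 90%, the standard error is 0.130 pooled (0.117 unpooled) and the ratio is 3.09 (3.43). Power under the named tests is 83.3% (Fisher), 83.0% (continuity-corrected chi-square) or 91.1% (uncorrected chi-square). The claimed power is too high by about 8 to 16 percentage points.

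This rests on the protocol's own inputs, a two-sided 5% level and one binary outcome per patient. It does not show that Part B is too small, since the 80% target holds on these assumptions. It is a correction to a figure that readers rely on, worth making but not a threat to the design.

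**What to change.** Rewrite the Part B paragraph of Section 4.3 along these lines: with 25 patients per arm, assumed completeness of 50% and 90% and two-sided alpha 0.05, the standard error of the difference is 0.130 (pooled), and power is about 83% with Fisher's exact test, or about 91% with the chi-square test without continuity correction.

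- Delete 0.0948, 4.216 and 99%.
- Say that 80% is the target and the new figure is the power at 25 per arm.
- State which test the power refers to, and name the same test in Section 9.1. The choice moves power by about 8 points.
- Put the completeness rates and the enrolment statement in the language of assumption and intention, as Section 9.2 already does for the rates.
- If the primary analysis is to compare per-patient completeness, as Section 9.2's definition suggests, replace the binary figures with the power of that test and state the assumed between-patient standard deviation.

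The cost is one corrected paragraph and a less favourable power figure. No additional patients are needed.
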